#### 3.6.3 Additional safety assessments

#### 3.6.3.1 Laboratory variables, vital signs and electrocardiograms (ECGs)

The following laboratory variables, vital signs and electrocardiogram (ECG) variables will be analyzed. They will be converted into standard international units.

- Hematology and coagulation:
  - Red blood cells, platelets and coagulation: hemoglobin, hematocrit, red blood cell count, platelet count, prothrombin time (expressed as international normalized ratio [INR]) and activated partial thromboplastin time (aPTT).
  - White blood cells: white blood cell (WBC) count, neutrophils, lymphocytes, monocytes, basophils, eosinophils.
- Clinical chemistry:
  - Metabolism: glucose, total protein and albumin.
  - Electrolytes: sodium, potassium, phosphate and corrected calcium. Corrected calcium (mmol/L) will be derived using the following formula: measured total calcium (mmol/L) + 0.8 x 0.25 × (4.0 [serum albumin (g/L) × 0.1]), where 4.0 represents the average albumin level.
  - Renal function: creatinine, blood urea nitrogen (BUN), urea, estimated glomerular filtration rate (eGFR) by the Modification of Diet in Renal Disease (MDRD method.
  - Liver function: alanine aminotransferase (ALT), aspartate aminotransferase (AST), alkaline phosphatase (ALP), lactate dehydrogenase (LDH), total and direct bilirubin.
- Urinalysis:
  - Urinalysis dipstick: proteins, red blood cell count, white blood cell count, glucose, pH.
  - Urinalysis: protein assessed on 24 hour urine collection.
- Vital signs: temperature, pulse rate, systolic and diastolic blood pressure, weight and Eastern Cooperative Oncology Group (ECOG) Performance status (PS).
- ECG variables: heart rate, PR, QRS, QT, and corrected QTc (according to Fridericia).

Data below the lower limit of quantitation/detection limit (LLOQ) will be replaced by half of the LLOQ, data above the upper limit of quantification will be replaced by ULOQ value.

For hematological parameters and biochemistry parameters, local normal ranges (LLN, ULN) will be used for grading.

#### Quantitative analyses

For vital signs and ECG variables above, descriptive statistics for results and changes from baseline will be provided for each planned visit, and the worst value (minimum and/or maximum value depending on the parameter) during the on-treatment period. These analyses will be performed using local measurements.

For QRS and QTc variables, blood pressure and heart rate, mean changes from baseline with the corresponding standard error will be plotted over time.

# Analyses according to potentially clinically significant abnormalities (PCSA) and NCI grading

For laboratory variables, analyses according to NCI grading will be made based on NCI-CTCAE Version 5.0. In addition, for laboratory variables for which an NCI-CTCAE scale is not applicable, vital signs and ECG variables, PCSA analyses will be performed based on the PCSA list currently in effect at Sanofi at the time of the database lock.

Analyses according to PCSA and NCI grading will be performed based on the worst value during the on-treatment period, using all measurements (either local or central, either scheduled, nonscheduled, or repeated).

QTcF prolongation will be graded according to NCI-CTCAE Version 5.0. The frequency of participants in each grade of QTcF prolongation during the on-treatment period will be summarized. For participants with multiple occurrences of QTcF prolongation during the treatment, the maximum grade per participant will be used.

For laboratory variables, vital signs and ECG variables above, the incidence of participants with at least 1 PCSA during the treatment-emergent period will be summarized regardless of the baseline level and according to the following baseline status categories:

- Normal/missing
- Abnormal according to PCSA criterion or criteria

The number (%) of participants with QTcF abnormality worsening during the on-treatment period (worst value per participant) according to baseline value will be displayed.

For laboratory variables graded by NCI-CTCAE,

- The number (%) of participants with abnormal laboratory tests at baseline will be presented by grade.
- The number (%) of participants with abnormal laboratory tests during the treatmentemergent period will be summarized by grade. When appropriate, the number (%) of participants with abnormality of any grade and with Grade 3-4 abnormalities will be provided.
- For liver function, baseline status will be provided according to multiples of ULN.

For laboratory variables not graded by NCI-CTCAE nor by PCSA, the number (%) of participants with laboratory tests outside normal ranges will be provided.

For ECOG PS, the number (%) of participants in each grade (considering the worst grade during the TE period) will be provided according to baseline.

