 - Duration of response will be summarized for the subgroup of participants who achieve confirmed objective response on the all-treated population with descriptive statistics using Kaplan-Meier methods. The median DOR and associated 95% CI will be provided.
 - Progression-free survival will be summarized on the all-treated population using Kaplan-Meier methods. The median PFS times and associated 95% CI will be provided, along with probabilities of being progression-free at different time points.
 - Disease control rate will be summarized on the all-treated population using descriptive statistics and 95% CIs will be provided using the Clopper-Pearson method. As a supplementary analysis, DCR will also be summarized on the activity population.
- **Analysis of safety endpoints:**
 - Number and percentage of participants experiencing TEAEs by primary system organ class (SOC) and preferred term will be summarized by NCI-CTCAE V5.0 Grade (all grades, and Grade ≥ 3) on the all-treated population. Similar summaries will be prepared for TEAEs related to IMP, TEAEs leading to permanent full/partial intervention discontinuation, TEAEs leading to dose modification or dose interruption, serious TEAEs, TEAEs with fatal outcome, adverse events of special interest (AESIs), and AEs/SAEs occurring during the posttreatment period. In addition, the number (%) of participants with any Grade 5 AE (TEAE and posttreatment) will be summarized.
 - Hematology and clinical chemistry results will be graded according to the NCI-CTCAE V5.0, when applicable. Number and percentage of participants with laboratory abnormalities (all grades and by grade) using the worst grade during the on-treatment period will be provided on the all-treated population.

Data Monitoring/Other committee: Yes

[figure not shown]
Study Committee (SC; Part 1)

The SC includes the Investigators or designees and Sponsor team members and, when appropriate, ad hoc experts. The SC will have regular meetings every 2 weeks during Part 1 (safety run-in phase) of the study.

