
 To assess the safety and tolerability of tusamitamab ravtansine loading dose Q2W in combination with ramucirumab To assess the durability of the response to treatment with tusamitamab ravtansine loading dose Q2W in combination with ramucirumab To assess progression-free survival (PFS) of tusamitamab ravtansine loading dose Q2W in combination with ramucirumab To assess the disease control rate (DCR) of tusamitamab ravtansine loading dose Q2W in combination with ramucirumab To assess the pharmacokinetics (PK) of tusamitamab ravtansine loading dose Q2W and ramucirumab when given in combination To assess the immunogenicity of tusamitamab ravtansine loading dose Q2W when given in combination with ramucirumab 	
 Incidence of treatment-emergent adverse events (TEAEs), serious adverse events (SAEs), and laboratory abnormalities according to the National Cancer Institute (NCI) Common Terminology Criteria for Adverse Events (CTCAE) V5.0 Duration of response (DOR), defined as the time from first documented evidence of CR or PR until progressive disease (PD) determined per RECIST 1.1 or death from any cause, whichever occurs first Progression-free survival, defined as the time from the first investigational medicinal product (IMP) administration to the date of the first documented disease progression or death due to any cause, whichever comes first Disease control rate, defined as the proportion of participants with confirmed CR or PR or SD as BOR per RECIST 1.1 Pharmacokinetic parameters of tusamitamab ravtansine and ramucirumab Incidence of antitherapeutic antibodies (ATAs) against tusamitamab ravtansine
Exploratory	

 To explore circulating carcinoembryonic antigen (CEA) as a potential biomarker for activity and to evaluate circulating CEA levels at prescreening 	
 Circulating CEA at prescreening, screening, during the treatment period and during the follow-up period

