- E 25. Washout period before the first administration of study intervention of less than 3 weeks or less than 5 times the half-life, whichever is shorter, for prior antitumor therapy (chemotherapy, targeted agents, immunotherapy and radiotherapy, or any investigational treatment).

- E 26. Poor coagulation as defined by International Normalized Ratio (INR) ≥ 1.5 or prothrombin time (PT) $\geq 1.5 \times$ upper limit of normal (ULN) and partial thromboplastin time/activated partial thromboplastin time (PTT/aPTT) $\geq 1.5 \times$ ULN, unless the participant is receiving anticoagulation therapy. Participants receiving warfarin must be switched to low-molecular-weight heparin and must achieve a stable coagulation profile prior to the first IMP administration.

Prior/concurrent clinical study experience

- E 27. Previous enrollment in this study, current participation in any other clinical study involving an investigational study treatment, or any other type of medical research.

Diagnostic assessments

- E 28. Poor organ function as defined by any one of the following prior to IMP administration:
- a) Serum creatinine $>1.5 \times$ ULN or estimated glomerular filtration rate (eGFR) <60 mL/min/1.73 m² as estimated using a Modification of Diet in Renal Disease (MDRD) formula.
 - b) Total bilirubin $>1.0 \times$ ULN (excluding congenital conjugation disorders [Gilberts], for whom total bilirubin $\leq 3.0 \times$ ULN, with direct bilirubin $\leq 1.5 \times$ ULN, is allowed).
or
aspartate aminotransferase (AST), alanine aminotransferase (ALT) $>2.5 \times$ ULN (In case of documented liver metastasis, AST, ALT $<5 \times$ ULN is allowed).
 - c) Neutrophils $<1.5 \times 10^9$ /L, platelet count $<100 \times 10^9$ /L, or hemoglobin <9 g/dL (blood infusion-free for at least 2 weeks).
- E 29. Urine dipstick or routine analysis indicating proteinuria of 2+ or higher, unless a 24 hour urine collection demonstrates <1000 mg of protein.

Other exclusions

- E 30. Accommodation in an institution because of regulatory or legal order (eg, prisoners or participants who are legally institutionalized).
- E 31. Any country-related specific regulation that would prevent the participant from entering the study - see Appendix 8 ([Section 10.8](#)) of the protocol (country-specific requirements).

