9.3.5.2 Laboratory variables, vital signs and electrocardiograms (ECGs)

Quantitative analyses

For vital signs and ECG variables, descriptive statistics for results and changes from baseline will be provided for each planned visit, and the worst value (minimum and/or maximum value depending on the parameter) during the on-treatment period. These analyses will be performed using local measurements.

Analyses according to Potentially Clinically Significant Abnormalities (PCSA) and NCI grading

For laboratory variables, analyses according to NCI grading will be made based on NCI-CTCAE version 5.0. In addition, for laboratory variables for which NCI-CTCAE scale is not applicable, vital signs and ECG variables, PCSA analyses will be performed based on the PCSA list currently in effect at Sanofi at the time of the database lock.

Analyses according to PCSA and NCI grading will be performed based on the worst value during the treatment-emergent period, using all measurements (either local or central, either scheduled, nonscheduled or repeated).

For laboratory variables, vital signs and ECG variables, the incidence of participants with at least one PCSA during the treatment-emergent period will be summarized regardless of the baseline level and according to the following baseline status categories:

- Normal/missing
- Abnormal according to PCSA criterion or criteria

For laboratory variables graded by NCI-CTCAE v5.0.

- The number (%) of participants with abnormal laboratory tests at baseline will be presented by grade.
- The number (%) of participants with abnormal laboratory tests during the treatment-emergent period will be summarized by grade. When appropriate, the number (%) of participants with abnormality of any grade and with Grade 3-4 abnormalities will be provided.

For ECG, the incidence of participants with at least one abnormal ECG during the treatment-emergent period will be summarized regardless of the baseline level and according to the following baseline status categories:

- Normal/missing
- Abnormal

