#### Visual acuity test

Analyses are done on the best corrected visual acuity (BCVA) assessed using Snellen Chart method.

Frequency tables on BCVA measured during the on-treatment period will be performed separately on all participants and on participants who experienced at least one treatment-emergent corneal event:

- On the worst change from baseline: No worsening versus baseline (no line decrease), Worsening versus baseline (1 to 3 lines decrease versus baseline, or >3 lines decrease versus baseline).
- On the worst absolute value: No change versus baseline, Worsening versus baseline (BCVA equals to 20/40 or better, BCVA worse than 20/40 up to 20/200, BCVA 20/200 or worse).
- On the CTCAE worst vision decrease: BCVA equals to 20/40 or better or 1 to 3 lines decrease versus baseline, BCVA worse than 20/40 up to 20/200 or >3 lines decrease versus baseline, BCVA 20/200 or worse.

• For participants who had worsening versus baseline (at least one line decrease) on BCVA, the worst outcome on the last BCVA will be displayed: Recovered to baseline, Not recovered to baseline, Lost to follow-up or dead with ongoing corneal events.

A participant will be considered as lost to follow-up if the participant discontinued the study and did not perform any follow-up visit.

A shift table of the category of the last BCVA value (Normal (20/20 or better), worse than 20/20 up to 20/40, worse than 20/40 up to 20/200 or 20/200 or worse) versus the category of the worst BCVA value (20/40 or better, worse than 20/40 up to 20/200, 20/200 or worse) will be performed for participants who experienced at least one treatment-emergent corneal event.

For the summary table on participants who experienced at least one treatment-emergent corneal event, the worst value and the worst change from baseline are measured during any of the treatment-emergent corneal events experienced by the participant (between start date and end date of the corneal events). For summary table on all participants, all on-treatment BCVA values are considered.

The worst classification between the laterality will be considered for the worst absolute value, the worst change from baseline and the last value separately even if not measured on the same eye. If the worst absolute value is the same for both eyes, then the eye with the worst change from baseline is considered, and if identical, then the eye with the worst last value is considered.

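### CTCAE-graded laboratory tests are tabulated separately at baseline and on treatment, so any-grade and low-grade on-treatment rates include unchanged entry abnormalities and the number of participants whose grade rose is not reported

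*SAP*

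**What the plan says.** The secondary safety endpoint in Protocol Section 3 covers adverse events "and laboratory abnormalities according to the National Cancer Institute (NCI) Common Terminology Criteria for Adverse Events (CTCAE) V5.0". The synopsis says how the laboratory part is reported: "Number and percentage of participants with laboratory abnormalities (all grades and by grade) using the worst grade during the on-treatment period will be provided".

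For CTCAE-graded tests, SAP 3.6.3.1 plans two one-way summaries. At baseline: "The number (%) of participants with abnormal laboratory tests at baseline will be presented by grade". On treatment, the matching sentence in Protocol 9.3.5.2 reads "The number (%) of participants with abnormal laboratory tests during the treatment-emergent period will be summarized by grade", with any-grade and Grade 3-4 counts where appropriate. The value entering the second table is the worst on-treatment value. Nothing requires it to be worse than baseline.

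Change-from-baseline statistics are planned for vital signs and ECG, not for laboratory variables. Elsewhere the SAP does compare participants with their own baseline:

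- QTcF: "The number (%) of participants with QTcF abnormality worsening during the on-treatment period", shown according to baseline value.
- ECOG performance status: worst grade according to baseline.
- Visual acuity (SAP 3.6.3.2): worst change from baseline, and "A shift table of the category of the last BCVA value" against the worst value.

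**The concern.** Some laboratory abnormality is permitted at entry. Protocol 5.2 (E28) excludes "hemoglobin <9 g/dL (blood infusion-free for at least 2 weeks", so a participant with hemoglobin between 9 g/dL and the lower limit of normal can enroll. SAP 3.6.3.1 says that "local normal ranges (LLN, ULN) will be used for grading", so such a participant is already abnormal at baseline. If the value does not move, the same participant is counted again in the on-treatment table.

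The study has one arm, so no control group nets out pre-existing abnormality and each participant's own baseline is the only internal reference. Anemia counts are likely to be read closely: cytopenia is a listed potential risk of tusamitamab ravtansine, and the benefit-risk text names anemia among the paclitaxel toxicities that the new combination might reduce. A reader who takes the any-grade on-treatment rate as a measure of worsening would overstate it.

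**Working it through.** **Size of the permitted band.** The generic lower limits for hemoglobin in SAP Appendix 5 are 135 g/L (men) and 120 g/L (women). The entry floor is 90 g/L. By those ranges the permitted abnormal band is 135 − 90 = 45 g/L for men and 120 − 90 = 30 g/L for women. Actual grading uses local limits.

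**What the two tables identify.** Let B_k and T_k be the numbers at Grade k or above at baseline and at worst on-treatment value. The excess is E_k = T_k − B_k, which equals the number newly reaching Grade k minus the number falling below it. If nobody improves, E_k is exactly the number newly reaching Grade k. The number of distinct participants whose grade rose, W, is then only bounded: it is at least the largest E_k (one person may cross several thresholds) and at most the sum of the E_k (each crossing by a different person).

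**Inputs.** N = 38 is the approximate maximum treated (Protocol 9.1, SAP Section 4). The documents give no baseline prevalences, so the margins below are assumptions, listed as Grades 0/1/2/3.

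| Case | Baseline | Worst on treatment | Any grade on treatment | E_1, E_2, E_3 | W, no improvement |
|---|---|---|---|---|---|
| a | 27/9/2/0 | 22/11/4/1 | 16/38 = 42% | 5, 3, 1 | 5 to 9 |
| b | 19/15/4/0 | 15/15/7/1 | 23/38 = 61% | 4, 4, 1 | 4 to 9 |
| c | 11/20/7/0 | 8/19/9/2 | 30/38 = 79% | 3, 4, 2 | 4 to 9 |

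An integer program with the margins fixed and improvement excluded gives the same limits. Both ends of case (b) can be reached:

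- W = 4: three participants go from Grade 0 to 2 and one from 0 to 3. The margins become 15/15/7/1.
- W = 9: four go from 0 to 1, four from 1 to 2 and one from 2 to 3. The margins become 15, 15+4−4 = 15, 4+4−1 = 7 and 1.

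**Unchanged abnormalities inside the any-grade count.** With no improvement, the on-treatment abnormal count equals W plus those abnormal at entry and unchanged. The unchanged group is 16 − 9 to 16 − 5 = 7 to 11 of 16 in (a), 14 to 19 of 23 in (b) and 21 to 26 of 30 in (c).

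**Sensitivity, case (b).** If all 19 baseline-abnormal participants stay abnormal but may fall a grade, W is 4 to 12. Twelve arises with four going 0 to 1, seven 1 to 2, one 2 to 3 and three 2 to 1. The number newly abnormal is still exactly 19 − 15 = 4. With improvement unrestricted, W is 4 to 23.

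**Where the tables suffice.** With no improvement, 19/19 at Grades 0/1 becoming 15/23 gives exactly 4, and identical tables give exactly 0.

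**Results already free of the problem.** Protocol 8.2.7.5 equates Grade 3 or higher liver enzymes with more than 5 × ULN, and entry bars AST/ALT at that level. Appendix 6 puts Grade 2 neutropenia below 1.5 × 10⁹/L, and entry bars that. Bilirubin above ULN is barred except in Gilbert's. On-treatment results at those levels are therefore already worsenings.

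**The case against.** The strongest reply is that the endpoint is incidence of laboratory abnormality by worst on-treatment grade, and the plan delivers it with the baseline table alongside. No count of worsening is promised. If abnormalities persist, the excess over baseline at each threshold is exact, and so is the number reaching Grade 3 or above when none are at Grade 3 at baseline, as in all three cases. This stands. It rules out a reading that a reader might infer, namely that the planned tables say nothing about worsening. What they lack is the count of distinct participants whose grade rose.

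A second reply concerns the potentially clinically significant abnormality (PCSA) analyses, which are split by baseline status. A reader might infer that CTCAE-graded tests never receive that split, because the SAP limits PCSA for laboratory variables to those without a CTCAE scale. The documents do not support so firm a statement. The liver-injury part of SAP 3.6.3.1 applies PCSA to each liver function test, with return to baseline status, and liver baseline status is also given in multiples of ULN. That is partial cover for liver tests. The PCSA list is not in the documents, so hemoglobin is unsettled. In any case a threshold split that pools missing baseline with normal is not a grade comparison.

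A third reply is that worsening appears as adverse events. Protocol 10.3.1 includes laboratory results that worsen from baseline if judged clinically significant, and SAP Table 9 selects hematological events by a cytopenia query. This covers clinically significant cytopenias. It does not cover low-grade shifts that are judged not significant, or those attributed to the underlying disease and not more severe than expected (Protocol 8.2.6).

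**Conclusion.** The point holds and is minor. As written, the on-treatment rule counts unchanged entry abnormalities in the any-grade and low-grade rates of a named secondary endpoint, chiefly for hemoglobin. Net excess over baseline can be recovered at each threshold. The number of distinct participants whose grade rose cannot, except in simple patterns. In the assumed examples it is known to within about a factor of two (4 to 9, or 5 to 9, of 38) if nobody improves, and less well if some do.

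These sizes rest on assumed margins and show what the tables can identify; they do not predict this trial. A reader might also infer that the Grade 3-4 counts are distorted. For AST/ALT and neutrophils the entry criteria exclude that. Dose-limiting toxicity, objective response and dosing decisions do not depend on these tables.

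**What to change.** In SAP 3.6.3.1, and in matching words in Protocol 9.3.5.2, add for each CTCAE-graded test:

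- a shift table of baseline grade by worst on-treatment grade, with a separate row for missing baseline;
- the number (%) of participants whose worst on-treatment grade exceeds their baseline grade (any increase, and increase to Grade 3-4), among those with a baseline value and at least one on-treatment value.

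Keep the existing all-participant counts. Do not group missing baseline with normal: each such participant who is abnormal on treatment would add 1/38 = 2.6 percentage points to the worsened count.

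The cost is SAP wording and a standard program run on data already collected, with one extra table per graded test. A shift table shows within-participant worsening; it does not separate drug effect from disease.
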